## 10.0 CRITERIA FOR EVALUATION AND ENDPOINT DEFINITIONS

A subject will be considered evaluable if they complete at least one year on the study, including both baseline and one-year study procedures. The outcome status (in terms of toxicity and biological response) of all eligible subjects will be reported. Subjects who begin treatment will be accounted for in the summaries of patient reported outcomes, regardless if they are considered evaluable or not.

### 10.1 Parameters to be Measured Prior to Initiation of Treatment

There will be two visits prior to the initiation of treatment: a screening visit to identify eligibility, and a baseline visit. With careful planning and coordination, these visits may be combined as described in Sections 9.1 and 9.2. At the screening visit, a history and physical, CBC (with platelets), comprehensive chemistry panel will be performed. A mammogram will also be performed at that time. (If the patient had a digital mammogram using a large-paddle digital mammography machine performed within 120 days, the patient is either postmenopausal or is premenopausal and can estimate the day in the menstrual cycle when the mammogram was performed, and a raw DICOM format image of that mammogram can be obtained, then their prior mammogram may be used as the study mammogram). A FSH and/or HCG level will be measured at that time if it is needed to determine menopausal status (see definition in Section 5.0). For confirmed screen-eligible subjects enrolled at FNA-participating sites, an RPFNA procedure will be performed within 60 days of the screening visit to establish baseline breast tissue markers (for patients consenting prior to protocol version 3/9/2015 and all previously consented patients as of 10/26/15). Blood will be drawn after an 8-hour fast and urine collected within 60 days of the screening visit to measure circulating biomarkers as outlined in the study calendar.

### 10.2 Specifications by Methods of Measurements

The same method and laboratory will be used to characterize each identified and reported biological endpoint at baseline and during follow-up (see Section 11.0).

### 10.3 Parameters to be Measured During Treatment

All evaluations will be measured per the study calendar schedule using the assay methodology outlined in Section 11.0. Analysis of results is fully described in Section 12.0.

The following are biological response endpoints:

1. Mammographic Breast Density
2. Tissue biomarkers of BC risk – Cytomorphology, proliferative (Ki67) index, and apoptotic (caspase) index
3. Insulin Growth Factors – IGF-1 and IGFBP-3

The following endpoints are measures of safety and tolerability:

1. Bone metabolism markers - serum bone specific alkaline phosphatase (BSAP) and urine N-telopeptide crosslinks (NTX)
2. Fasting lipid panel – total cholesterol, HDL-cholesterol, LDL-cholesterol, and triglycerides
3. Clotting propensity – anti-thrombin III (AT-III)
4. Symptom logs

## 11.0 SPECIAL INSTRUCTIONS

### 11.1 Mammographic Breast Density (MBD)

Mammograms will be collected within 120 days prior to treatment initiation and at one and two years after initiation of treatment as described in the study calendar. After a clinical reading by a local radiologist, who will evaluate density according to the ACR BIRAD scoring system used to determine eligibility, MBD will be determined from digital mammogram images by study radiologists experienced in breast imaging. This density assessment method, fully outlined below, yields a value expressed as a continuous percentage, which is more sensitive to modulation by an intervention than the categorical BIRADS density score. Thus, while BIRAD score will be used for determining eligibility, percent breast density will be subjectively evaluated by study radiologists, and objectively measured using area- and volume-based mammographic density software. The area-based software measurement will be the primary endpoint. MBD will be determined from each breast. If the patient had a history of DCIS or IEN prior to study entry, or if one breast had a baseline BIRAD density score of 1, only the contralateral breast measurement will be used for analysis. Otherwise, the two measurements will be modeled as described in the statistical section.

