## 5.2 Exclusion Criteria

Subjects will be excluded if any of the following characteristics are present:

- SMN other than those listed below diagnosed within 2 years of study entry. Patients with the listed indolent or pre-invasive neoplasms may be eligible if diagnosed within 2 years and all treatment was completed at least 6 months prior to registration:
  - non-melanoma cancers of the skin
  - thyroid cancer
  - cervical cancer confined to the cervix or cervical intraepithelial neoplasia (CIN)
  - ductal carcinoma in situ (DCIS) or breast IEN (includes atypical hyperplasia and LCIS)
  - superficial or non-invasive transitional cell carcinoma of the bladder

For women with a prior history of ductal carcinoma in situ (DCIS) or breast IEN, only one breast could have been involved and all therapy must have been completed at least 6 months prior to registration. In addition women with a prior history of invasive breast cancer may also be eligible, as long as only one breast was involved, they were diagnosed at least 2 years prior to study entry, and therapy was completed at least 6 months prior to study entry.

- Bilateral breast implants or status-post bilateral prophylactic mastectomy.
- Evidence of malignant breast disease on any form of breast imaging. The study only requires annual mammography; however, annual breast MRI is considered standard of care in this patient population (per COG or NCCN follow-up guidelines), and breast ultrasound may be indicated if a palpable lesion is detected on screening clinical breast exam. Abnormal imaging may require additional radiographs and/or breast biopsy. Patients who are found to have benign breast disease with or without atypia may continue on study as long as there is no evidence of malignancy. If there is evidence of malignancy, and only one breast is involved, they may be reapproached 6 months after completion of therapy for consideration of the trial.
- Baseline categorical mammographic density scored as BIRAD 1, or extremely fatty, in both breasts (see Figure 9). If the patient has a prior history of IEN (DCIS, LCIS, or atypical hyperplasia), the contralateral breast must not have a mammographic density score of BIRAD 1. This determination will be made at the local site.

- Current or recent use (within 6 months of registration or baseline mammogram, whichever is first) of any of the following hormonal agents:

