differences at t1 and t2, and their significance tested using a 2-df chi-square test. Low dose tamoxifen will be considered effective if 1) the 2-df test is significant and the expected RTMBD is lower both at t1 and t2 or at t2 compared to that of the placebo group, or 2) the interaction term at t2 is significant and the expected RTMBD there is lower than that of placebo. It should be noted that because common fixed effects for intercept and time coefficients are assumed for both breasts, the expected RTMBD is the same for both breasts within a treatment group. This model enables use of the data from both breasts to estimate the common treatment effect while accounting for the between-breast correlation and the correlation among repeated measurements over time within a woman. The validity of these restrictions, e.g. common intercept and treatment effect between left and right breast, while biologically reasonable, will be examined and tested. This method also enables women with incomplete RTMBD data, i.e. data from only one breast or missing data at specific time points, to be included in the analysis. In addition to the unstructured mean model, we will also fit a linear model in time, with an interaction of time by group indicator to allow for treatment difference. A significant time by group interaction, with a larger negative slope for the low dose tamoxifen group compared to placebo, will indicate the effectiveness of low dose tamoxifen in reducing MBD.

In addition to unadjusted analyses which are appropriate under the randomization principal, adjusted analysis also will be performed. Significantly imbalanced covariates and covariates known to be prognostic for BC, such as radiation dose, age at irradiation, premature menopause, and family history for BC, will be incorporated in the longitudinal models before including and testing the time by treatment group interaction.

To address potential noncompliance, we will also conduct an as-treated analysis, considering patients' actual treatment uptake. Instead of the treatment indicator (PBO or LDTAM), we will include adherence rate, i.e. 0 for PBO and a number between 0 and 1 for LDTAM determined by pill count, in the LME model. Time-specific adherence rate and the overall adherence rate will be considered. If LDTAM is effective, we may expect to see a decrease in MBD with adherence rate.

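### Section 11.1 drops a breast with prior DCIS or IEN from the primary density analysis but keeps a conserved breast treated for invasive cancer

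*Combined protocol and SAP*

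**What the plan says.** Section 11.1 gives two triggers for dropping a breast from the primary endpoint. One applies "If the patient had a history of DCIS or IEN prior to study entry"; the other reads "or if one breast had a baseline BIRAD density score of 1". In either case "only the contralateral breast measurement will be used for analysis". For everyone else the default is: "Otherwise, the two measurements will be modeled as described in the statistical section".

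Section 5.2 covers invasive disease in a sentence of its own: "In addition women with a prior history of invasive breast cancer may also be eligible, as long as only one breast was involved". It adds that diagnosis must be at least 2 years, and the end of therapy at least 6 months, before study entry. The same section spells out IEN as DCIS, LCIS or atypical hyperplasia, so the term cannot be stretched to cover invasive cancer. Its density criterion excludes women who are BIRAD 1 in both breasts. It adds, for women with prior IEN only, that "the contralateral breast must not have a mammographic density score of BIRAD 1".

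Sections 12.4 and 12.5 contain no further rule removing a treated breast. The expected density course is the same on both sides "because common fixed effects for intercept and time coefficients are assumed for both breasts", and one treatment effect is estimated from both breasts.

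**The concern.** The sponsor has already decided that a breast with DCIS or IEN should not count towards the primary endpoint. Leaving invasive cancer off the list reverses the natural order: the less serious history removes the breast and the more serious one leaves it in, and no reason is given.

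If a treated breast responds less to tamoxifen, including it pulls the estimated common treatment effect towards zero. If its density follows a different course for other reasons, it adds noise. There is also a procedural cost. The analyst would have to choose between the literal rule and its evident intent, and making that choice after unblinding would be a post-hoc decision about primary-endpoint data.

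**Working it through.** **Step 1: follow the rule for a woman with prior unilateral invasive cancer and no recorded DCIS or IEN.**

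| Treated breast | Untreated breast | What 11.1 does as written |
|---|---|---|
| Conserved, not BIRAD 1 | Not BIRAD 1 | Both breasts modelled; treated breast included |
| Conserved, not BIRAD 1 | BIRAD 1 | Untreated breast dropped; treated breast is the only one analysed |
| Conserved, BIRAD 1 | Not BIRAD 1 | Treated breast dropped by the BIRAD 1 trigger; no problem |
| Removed | Not BIRAD 1 | No image on that side; the available breast is used; no problem |
| Removed | BIRAD 1 | Not clearly excluded by 5.2, since BIRAD 1 is required in both breasts; 11.1 then leaves nothing to analyse |

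The concern is therefore limited to the first two rows. A woman whose invasive cancer came with recorded DCIS or IEN is also caught by the existing rule.

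**Step 2: reproduce the plan's sample size.** Inputs from Section 12.5 are an effect size of 0.25 SD at year 2 on the square-root scale, compound symmetry with correlation 0.8, two-sided alpha 0.05 and power 0.80. For a linear trend over three visits the contrast SD is √(2 × (1 − 0.8)) = 0.632.

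n per arm = 2 × [0.632 × (1.960 + 0.842) / 0.25]² = 100.5, against 100 in the plan. At 100 per arm the standardised effect is 0.25 / (0.632 × √(2/100)) = 2.795, and power is Φ(2.795 − 1.960) = 79.8%. The plan's figure reproduces.

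**Step 3: dilution.** Section 12.5 takes the mean of the two breasts as the response. Let *f* be the share of women contributing a conserved treated breast alongside a normal one, and *L* that breast's response as a fraction of normal. The effect is multiplied by d = 1 − f(1 − L)/2, and power is Φ(2.795 × d − 1.960). Both *f* and *L* are assumptions; the documents give neither.

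| f | L | d | Power at 100 per arm |
|---|---|---|---|
| 0 | – | 1 | 79.8% |
| 2% | 0.5 | 0.995 | 79.4% |
| 2% | 0 | 0.990 | 79.0% |
| 5% | 0.5 | 0.9875 | 78.8% |
| 5% | 0 | 0.975 | 77.8% |
| 10% | 0.5 | 0.975 | 77.8% |
| 10% | 0 | 0.950 | 75.7% |

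For the last row: 2.795 × 0.95 = 2.655, and Φ(2.655 − 1.960) = 75.7%.

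The 79.8% benchmark supposes two normal breasts in every woman. Under the fix these women contribute one breast, which is less precise than the mean of two, so the fix would not recover the whole difference. The documents give no between-breast correlation, so this loss is not quantified here. The table also leaves out the second row of Step 1, where the treated breast carries full weight for that woman.

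**The case against.** The strongest reply is that this is a drafting slip with little effect, and much of that stands.

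- **The affected group is narrow.** Section 2.1 puts cumulative breast cancer incidence after chest radiation at 12.9% to 13.9% by age 40 and 20% to 22% by 45, and the source cohort's median age is given as 35 or 36. Eligibility then requires unilateral disease, the time limits in 5.2, and no endocrine agent in the preceding 6 months. Women who lost the breast also fall out. A reader might take the 20% figure as the share of trial women affected, which with no response would put power at 71.1% (d = 0.90). The documents do not support that: it is lifetime incidence to age 45 before any of these filters. Enrolment could be selective, so this is inference and not a count.
- **The model absorbs part of it.** The breast-specific random effects in 12.4 take up a stable difference in density level. Only a different course or response over time affects the contrast. A reader might infer that any treated breast invalidates the model; that goes too far.
- **Assumptions will be checked.** Section 12.4 says the restrictions across breasts will be examined and tested. Left versus right is the only example named, though, and treated breasts may lie on either side, so that comparison would not isolate them.
- **Randomisation protects the comparison.** A reader might infer a biased treatment effect between arms. Nothing in the documents points to that.

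None of this removes the textual gap. Nor is invasive history obviously the rarer one: in two series in Table 1, invasive tumours outnumber in-situ ones by 37 to 8 and 62 to 9, although atypical hyperplasia is not counted there.

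**Conclusion.** The gap is real. Sections 5.2 and 11.1, read together, put a conserved breast treated for invasive cancer into the primary endpoint, and in one configuration make it the only breast analysed. It applies only to women who kept a treated breast that was not BIRAD 1 and who had no recorded DCIS or IEN.

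The likely consequence is modest dilution and noise: a loss of about 0.4 to 4 percentage points of power from 79.8%, under assumed shares of 2% to 10% and half to no response. That a treated breast responds less is itself an assumption, consistent with the sponsor's handling of DCIS and IEN but not demonstrated in the documents. The stated sample size does not change. The point is worth correcting because the rule contradicts its own logic on the primary endpoint and the correction is cheap.

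**What to change.** 1. Before unblinding, amend the first trigger in Section 11.1 to read: *a history of DCIS, IEN or invasive breast cancer*.
2. State in 11.1 how an enrolled woman left with no analysable breast is handled. With the amended trigger, a woman with a treated breast on one side and BIRAD 1 on the other would lose both, which conflicts with the commitment in 12.4 to analyse every patient with baseline mammographic data. One option is for the primary analysis to use the untreated breast whatever its BIRAD score, with a sensitivity analysis using all available breasts.
3. Reconcile the BIRAD 1 criterion in Section 5.2 with this rule for future enrolment only. It cannot be applied to women already randomised.

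The cost is one breast's data for each affected woman, as already happens after DCIS or IEN. The mixed model accepts single-breast data, so these women stay in the analysis with somewhat less precision.

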#### 11.1.1 Digital mammogram handling and transfer:

Mammography images will be performed on digital mammography machines using large paddles. Serial mammograms for each patient will be performed at the same facility using the same machine whenever possible. Sites will save post-processed and pre-processed or raw mammography images whenever both are available. The pre-processed or raw image is also called the “for processing” image, and may require coordination with radiology staff to obtain before being cleared from the PACS system. The post-processed image (also called “for presentation” image) is the file typically displayed by a standard PACS system. Each digital image (up to 8 mammogram files per patient time point) should be de-identified (headers excluded) and submitted on CD-ROM to the address below within 28 days of the screening, Day 365, and Day 730 visits.

If the subject has been followed with screening breast MRI as part of their standard of care screening regimen, the full electronic MRI file from the last breast MRI procedure performed prior to starting study drug and any breast MRI procedures performed during the 2-year protocol treatment period will be saved in de-identified DICOM format. All clinical MRI series obtained during the pre-treatment breast MRI procedure will be submitted at the same time as the screening mammogram. All clinical MRI series obtained during all breast MRI procedures performed on protocol treatment (up to two annual exams per participant) may be submitted at the end of study with the Day 730 mammogram.

The CD-ROM will be labeled with the subject’s name, central participant ID, site, and the date of preparation of the CD-ROM. A **Breast Imaging Submission Form** will be submitted along with the CD-ROM, on which the CRA/CRN will specify the date(s) of procedure(s) and the imaging equipment used. The electronic MRI will only be referred to as needed in the case of a breast event on trial. The MRI may also be stored for future research.

Address for site submission of breast imaging:

[name], MPH  
ATTN: LDtam study coordinator  
UAB Division of Peds Hem/Onc  
[name]  
United States  
[contact]  
[contact]  
Email: [[contact]](mailto:[contact])

After the CD-ROM arrives, study staff at the coordinating center will remove any electronically embedded patient identifiers and procedure dates from the header of each image file. Then, film IDs will be assigned to each mammogram image, consisting of the participant ID plus a dummy code in random order with respect to timing. The procedure date for each mammogram will be tracked in a database that documents which dummy code was assigned to the serial images. Anonymized films will be sent to the study radiologists, organized in batches at multiple reading time points: when the 10th patient completes the study (initial data check), and subsequently when the 25th, 50th, 100th (halfway point), 150th, and the last patient completes the study.

MBD will be assessed in 12 batches (2 batches at each of the 6 reading time points) that contain all raw (batch A) and processed (batch B) films collected for 10-80 subjects (up to 320 films per reading time point). Views for 10% of subjects in each batch will be included in a subsequent batch to obtain a second reading to assess reader reliability.

11.1.2 MBD assessment:

MBD will be assessed by study radiologists using previously published area [65] and volumetric [66] software methods.

11.1.3 MBD quality assurance:

Since all subject identifiers and dates will be removed from the DICOM file prior to transfer, study radiologists will be blinded to treatment arm as well as timing of the mammograms. To minimize random measurement error, all mammograms from each subject will be read in the same session, but they will be in random order. A random 10% of subject's films will be read twice to estimate quality control, as described above. Results will be delivered electronically, according to the batching procedures described above.

11.2 **Breast tissue sampling**

Breast epithelia will be sampled at baseline and after the two-year treatment period. Normal breast epithelial tissue will be acquired via RPFNA, which is a well-tolerated procedure that has been found to yield adequate tissue for multiple biomarkers [52]. The RPFNA procedure is fully described below, as well as the assays planned for tissue specimens obtained. The tissue biomarkers will be considered as secondary endpoints.

**NOTE: The study was amended to discontinue this procedure for new patients consenting to the study (protocol version 3/9/2015) and all previously consented patients as of 10/26/15.**

### 11.2.1 RPFNA procedure

After local anesthesia, a 21-gauge needle attached to a 10-mL syringe will be used to sample normal breast glandular tissue of the upper outer and upper inner quadrants by entering just immediately adjacent to the areola at approximately 3 o'clock and 9 o'clock, varying the position slightly as needed to avoid superficial blood vessels. Tissue is probed deeply to sample the terminal lobular–duct unit, where most cancers are thought to arise, obtaining 8-10 aspirations per breast; half from the upper outer quadrant site and half from the upper inner quadrant site. After the procedure, cold packs are applied to the aspiration sites for approximately 10 minutes, the breasts and chest wall are firmly bound in gauze, and a tight-fitting sports bra was worn over the gauze wrap to minimize breast movement and to decrease the chance of hematoma formation. Performing the RPFNA procedure in this manner typically yields 1000 epithelial cells per cytology slide [94, 95]. Minimum epithelial cell yields to allow evaluation are 10 for cytomorphology and 25 for IHC per slide.

The RPFNA procedure is well tolerated by most women, with any temporary discomfort experienced typically relieved with acetaminophen. In a large study including 480 women, 408 of 439 women invited for a repeat aspiration (93%) agreed to a second procedure, with 225 (51%) doing so as soon as 6 months after the first procedure. Infection requiring oral antibiotics or large hematoma formation requiring surgical evacuation occurred in fewer than 1% of the procedures performed [94]. Women will be asked to stop any medication that they may be taking that might increase their chances of bruising for at least ten days prior to the procedure (aspirin, non-steroidal, anti-inflammatory, or anti-coagulant medications, as well as any herbal supplements). In addition, as long as there is no history of venous thromboembolism, they may be given vitamin K 10mg to take daily for 3 days prior to the procedure to avoid bleeding and hematoma formation. Patients should be offered lorazepam 2 mg for anxiety and be instructed to take it 30 minutes before the procedure if they feel they need it. In that case, they should arrange for transportation and avoid driving that day. Also, the patient should be provided with four extra-strength Tylenol after the procedure in case of discomfort.

